#### **Design overview**

Trial design, including number of arms	Two-arm, cluster randomised
Unit of randomisation	Teams of youth practitioners
Stratification variables	Local Authority

<sup>5 Evidence collected during the pilot trial showed that the observed characteristics of young people assigned to treated and control teams were well balanced, and that capacity and historical assignment were major drivers of assignment of young people to teams, as described in the next point below.

(if applicable)		
	variable	Conduct problems
Primary outcome	measure (instrument, scale, source)	A binary indicator for scoring in the high and very high range of the conduct problems subscale of the Strengths and Difficulties Questionnaires, taking the value 1 if the score is in the high or very high range and 0 otherwise. Measured as part of the endline young person survey, administered at week 20 after recruitment during a session with the practitioner.
Secondary outcome(s)Offending activity, regulation, social behaviours, hyp practitioner-report safety, prosocial b Continuous scores except offending a a binary indicator person offended a behaviours, hyper we will also use bin young person score and 0 otherwise.		Offending activity, mental wellbeing, emotional self- regulation, social connectedness, internalising behaviours, hyperactivity, self-reported and practitioner-reported perceptions of young person's safety, prosocial behaviour and prosocial identity. Continuous scores will be used for all outcomes except offending activity, which will be measured as a binary indicator taking the value 1 if the young person offended and 0 otherwise. For internalising behaviours, hyperactivity and prosocial behaviour, we will also use binary indicators taking value 1 if the young person scores in the high or very high range and 0 otherwise.
	measure(s) (instrument, scale, source)	Criminal activity: recorded arrest in Police National Computers during the period of 16 months after recruitment. Self-reported and practitioner-reported perceptions of young person's safety: Young person and practitioner versions of "Checkpoint. A safety scale for young people", which is an instrument to measure young people's perceptions of safety developed by the research team. Part of the endline

young person questionnaire, administered at week 20 after recruitment.

*Wellbeing*: The Short Warwick–Edinburgh Mental Well-being Scale (SWEMWBS). Part of the endline young person questionnaire, which is administered at some point between weeks 14 and 20 after recruitment.

*Emotional self-regulation*: Trait Emotional Intelligence Questionnaire – Adolescent Short Form (TEIQUE-ASF) – Self regulation subscale. Part of the endline young person questionnaire, administered at week 20 after recruitment.

Social connectedness: Social Connectedness Scale – Revised (SCS-R). Part of the endline young person questionnaire, administered at week 20 after recruitment.

Internalising behaviours: emotional difficulties and peer difficulties subscales of the SDQ measured at baseline and endline as part of the participant's surveys administered following recruitment and at week 20 after recruitment respectively.

*Hyperactivity*: hyperactivity subscale of the SDQ measured at baseline and endline as part of the participant's surveys administered following recruitment and at week 20 after recruitment respectively.

*Prosocial behaviours*: Strength and Difficulties prosocial behaviour subscale measured at baseline and endline as part of the participant's surveys administered following recruitment and at week 20 after recruitment respectively.

*Prosocial identity*: Pro-social Identity Scale (PIDS) measured at baseline and endline as part of the participant's surveys administered following

		recruitment and at week 20 after recruitment respectively.	
	variable	Conduct problems	
Baseline for primary outcome	measure (instrument, scale, source)	Indicator for scoring in the high or very high range of conduct problems scale from the Strengths and Difficulties Questionnaires.	
		Measured as part of the baseline participant's survey, administered in week 1 after recruitment, before the start of Your Choice.	
	variable	Social connectedness score, internalising behaviour, hyperactivity, prosocial behaviour and prosocial identity, self-reported and practitioner-reported perceptions of young person's safety.	
	measure (instrument, scale, source)	All measured as part of the baseline participant's survey, administered in week 1 after recruitment, before the start of Your Choice.	
Baseline for secondary		Social connectedness: The Social Connectedness Scale – Revised (SCS-R), survey of young person following consent before Your Choice starts (in some cases, some form of BAU work/support will have already been taking place).	
outcomes		Internalising behaviours: emotional difficulties and peer difficulties subscales of the SDQ.	
		Hyperactivity: hyperactivity subscale of the SDQ.	
		Prosocial behaviours : Strength and Difficulties prosocial behaviour subscale.	
		Prosocial identity : Pro-social Identity Scale (PIDS) measured.	
		Self-reported and practitioner-reported perceptions of young person's safety: Young person and practitioner versions of "Checkpoint. A safety scale	

for young people", which is an instrument to measure young people's perceptions of safety developed by the research team.

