#### What is Your Choice and how is it adapted?

Despite the promising evidence base, a common criticism of CBT has been an over reliance on the mechanistic application of a set of techniques, with a lack of emphasis of the importance of the therapeutic relationship (Wenzel, 2021). Consequently, the Your Choice programme prioritises time for investing in and nurturing relationships with young people through intensive contact. This is in acknowledgement of the needs of the cohort and that relationships that are safe, collaborative and trusting are likely to impact on engagement and outcomes (Thomson et al, 2007).

In addition to being informed by the principles and practices of CBT, the Your Choice programme is underpinned by a range of psychological theory and best practice principles relevant to working with adolescents at risk. This includes attachment and developmental theory and child first and trauma informed principles.

In accordance with child first principles, the Good Lives (Ward & Steward, 2003, cited in Barnao, 2022) and public health approach (Case and Browning, 2021) to reducing risk, Your Choice is a strengths-based programme, which is responsive to an individual's interests, values and aspirations and builds capabilities and strengths in order to reduce risks. Your Choice emphasises the importance of behavioural activation (a core component of CBT) to promote positive and pro social behaviour by i) providing access to positive alternatives and opportunities, ii) connecting young people with "safe" communities iii) disrupting and diverting young people away from unhelpful, unhealthy patterns of behaviour iv) empowering young people to identify with "routes out" of problematic or harmful behaviours

and/or situations. This is particularly important given that adolescence is a significant developmental phase relating to the formation of identity (Erikson, 1968).

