    - Have a more prosocial behaviour? The outcome of interest will be the SDQ prosocial behaviour scale, measured as part of the endline young person questionnaire in week 20 after recruitment.
  - Have a stronger prosocial identity? The outcome of interest will be the ProSocial Identity Scale, measured as part of the endline young person questionnaire

4. Do the impacts of being allocated to a team trained in Your Choice differ by gender, age, ethnicity, special education needs, level of risk assessed by the practitioner?

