Prosocial behaviour: measured by the prosocial scale of the Strengths and Difficulties Questionnaire, which is part of the endline young person's survey taken in week 20 after recruitment. This measure will provide insight into whether the impact of the intervention may be partly driven by changes in prosocial behaviour, as hypothesized in the logic model.

Prosocial identity: measured by the Pro-social Identity Scale (PIDS), which is part of the endline young person's survey taken in week 20 after recruitment. This measure will provide insight into whether the impact of the intervention may be partly driven by changes in prosocial identity, as hypothesized in the logic model.

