Number of participants	Due to lower-than-expected recruitment and higher than expected attrition, in January 2025 the recruitment period was extended to the end of February 2025. To inform this decision, we re-estimated the number of participants based on recruitment to date and new information from the Local Authorities and revised the number of participants down to 1,563 young people recruited across the internal pilot and efficacy trial recruited between August 2023 and end of February 2025. Across teams that have ever been randomised, this included an expected 1,402 young people recruited between August 2023 and February 2025 and 161 young people who were recruited during the internal pilot phase (82 of whom we have endline data for). We expect a 70% data completion rate across the internal pilot and efficacy trials, which sets the overall sample for impact evaluation at 1,094.		
Primary outcome and data source	Indicator for scoring in the high or very high range of the conduct problems subscale of the Strengths and Difficulties Questionnaires (SDQ). The high and very high range threshold is defined by the SDQ's four-fold categorisation.		
	The SDQ is taken at the start and end of the young person's pathway through the programme, at weeks 1 and 20 after		

	recruitment. In both cases, they are administered during a session with the practitioner, as part of the baseline and endline surveys. Some small variation in the timing of these surveys is allowed, to accommodate differing start and end dates for the programme and convenience in scheduling meetings between participants and practitioners. Below we will be referring to week 1 and 20 as expected times for these surveys.
	Criminal activity : Indicator for recorded arrest in Police National Computers during first 16 months after recruitment (allowing for 4-months treatment plus 1 year following treatment).
	Self-reported and practitioner-reported perceptions of young person's safety: Young person and practitioner versions of "Checkpoint. A safety scale for young people", which is an instrument to measure young people's perceptions of safety developed by the research team. Measured at baseline and endline as part of the participant's and practitioner's surveys (weeks 1 and 20 after recruitment, respectively).

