#### Secondary outcome analysis

Analysis of secondary outcomes will follow the same approach as for primary outcomes described above. To account for multiple hypothesis testing given the large number of secondary outcomes, we will calculate p-values using the step-down procedure of Romano and Wolf [2016]. The Romano-Wolf correction (asymptotically) controls the familywise error rate (FWER), that is, the probability of rejecting at least one true null hypothesis in a family of hypotheses under test. This correction is considerably more powerful than earlier multiple testing procedures such as the Bonferroni and Holm corrections, given that it takes into account the dependence structure of the test statistics by resampling from the original data. To implement it, we will use Stata's rwolf2 command, report unadjusted and adjusted *p*-values, and determine statistical significance of the results based on adjusted *p*-values below 0.05.

The estimating equation for ITT impacts for young period i will be of the form:

$$Y_{i1} = \beta_0 + \beta_1 D_i + \beta_2 X_i + \beta_3 Y_{i0} + strata \ fixed \ effects + u_i$$

where, as before,  $Y_{i1}$  is the secondary outcome of interest, and  $Y_{i0}$  is the baseline value for that same outcome (if any),  $D_i$  is an indicator for treatment assignment,  $X_i$  are any baseline characteristics of the young person for which we find statistically significant imbalances between treated and control groups, and  $u_i$  is an error term.

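### The SAP gives the prosocial binary indicator the same high-or-very-high rule as the SDQ difficulty subscales, so as written it marks the favourable end of the scale or a band that is not defined

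*SAP*

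**What the plan says.** The Design overview table of the SAP defines the primary conduct-problems indicator as "taking the value 1 if the score is in the high or very high range and 0 otherwise". In the row for secondary outcomes it says "Continuous scores will be used for all outcomes", with offending as the exception. It then adds dichotomised versions of three outcome groups under a single rule. The sentence, which covers the internalising and hyperactivity scores too, reads in part: "prosocial behaviour, we will also use binary indicators taking value 1 if the young person scores in the high or very high range". All other young people are coded 0.

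The title table of the SAP says where the bands come from: "The high and very high range threshold is defined by the SDQ's four-fold categorisation". That sentence describes the conduct problems subscale. The protocol's section on the primary outcome also mentions the four-fold categorisation only in that setting. Neither document sets out bands for the prosocial subscale.

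The protocol does show which direction is favourable. Its description of the programme says that behavioural activation is used "to promote positive and pro social behaviour". Research question 3 asks whether treated young people "Have a more prosocial behaviour? The outcome of interest will be the SDQ prosocial behaviour scale". The section on secondary outcomes says that this outcome is "measured by the prosocial scale of the Strengths and Difficulties Questionnaire" and presents a change in it as one route by which the programme may work.

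On modelling, the SAP says "Analysis of secondary outcomes will follow the same approach as for primary outcomes described above". It adds no recoding and no note on direction for the prosocial indicator.

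**The concern.** A rule that makes 1 the adverse state on a difficulty scale makes 1 the favourable state on a strength scale. Under the shared sentence, the internalising and hyperactivity indicators flag young people with problems. The prosocial indicator flags those doing well, and those with low prosocial behaviour are coded 0 together with those in the middle of the scale.

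This goes beyond the sign of a coefficient. A cut at the upper end is not the complement of a cut at the lower end, so the choice of end changes the estimate, its standard error, the risk ratio and the p-value. If the end and the cut-off are left open until the data are seen, there is an avoidable analyst choice on a secondary outcome.

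The rule also sits badly with the reasoning that the protocol gives for its primary outcome. There, the score is dichotomised at the problem end because that is the margin where the programme is expected to work. Read literally, the prosocial indicator looks at the opposite margin.

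**Working it through.** No sample size, power or error-rate figure rests on this indicator, so there is no stated figure to reproduce. The check compares the definitions and then illustrates the consequence.

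**Step 1: direction of each scale that gets a binary version.**

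- Conduct problems (primary): 1 = high or very high, which is adverse.
- Internalising (emotional and peer difficulties): same rule, adverse.
- Hyperactivity: same rule, adverse.
- Prosocial behaviour: same rule, but the protocol treats more of it as the gain, so 1 is favourable.

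One of the three secondary groups under the shared rule therefore runs against the other two, and against the primary outcome.

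**Step 2: is this reversed or resolved elsewhere?** The SAP sections on secondary outcome analysis and presentation of outcomes, and the protocol's accounts of the primary and secondary outcomes, contain no reverse scoring, no low prosocial band and no guide to the sign. Two readings remain. Either high or very high means high scores, and the indicator marks the favourable end. Or it was meant as a risk label, in which case the documents do not say which scores fall in it and the indicator is undefined.

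**Step 3: size under the literal reading.** Assumptions, none from the documents: a normal prosocial score with SD 1, a favourable shift *d* of 0.1 or 0.2 SD, and a control share *q* flagged of 10% to 60%. Φ is the normal distribution function and z its quantile.

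- Upper-end indicator, treated share: 1 − Φ(z(1−q) − d)
- Lower-end indicator, treated share: Φ(z(q) − d)
- Risk ratio: treated share divided by q

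For d = 0.2 and q = 0.30, z(0.70) = 0.524:

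- Upper end: 1 − Φ(0.324) = 0.373, so +7.3 points and a risk ratio of 0.373/0.300 = 1.24.
- Lower end: Φ(−0.724) = 0.234, so −6.6 points and a risk ratio of 0.234/0.300 = 0.78.
- A problem scale improved by the same 0.2 SD, cut at its upper end: 1 − Φ(0.724) = 0.234, so −6.6 points, matching the lower-end prosocial result.

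| d | q | Upper end, treated | RR | Lower end, treated | RR |
|---|---|---|---|---|---|
| 0.1 | 0.10 | 0.119 | 1.19 | 0.084 | 0.84 |
| 0.1 | 0.30 | 0.336 | 1.12 | 0.266 | 0.89 |
| 0.1 | 0.60 | 0.638 | 1.06 | 0.561 | 0.93 |
| 0.2 | 0.10 | 0.140 | 1.40 | 0.069 | 0.69 |
| 0.2 | 0.30 | 0.373 | 1.24 | 0.234 | 0.78 |
| 0.2 | 0.60 | 0.675 | 1.12 | 0.521 | 0.87 |

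Across these assumptions a true benefit gives risk ratios of 1.06 to 1.40 on the upper-end indicator and 0.69 to 0.93 on the lower-end one.

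**Step 4: benefit confined to the low end.** Suppose the low share is 20% in controls and 10% in treated, the difference has moved to the middle, and the top share is equal in both arms. The lower-end indicator shows 0.10 − 0.20 = −10 points. The upper-end indicator shows 0, because everyone who moved goes from 0 to 0.

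**The case against.** Much of the case on the other side stands.

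- An upper-end indicator can be analysed and fits the wording of research question 3, which asks about more prosocial behaviour. Making 1 the adverse state on every SDQ indicator is a convention that the SAP does not adopt. The SAP does not declare an upper-end intention either.
- Every dichotomy hides some movement. A low-end indicator would miss movement from average to high just as an upper-end one misses movement from low to average. The argument for the low end rests on consistency with the rationale for the primary outcome.
- That rationale is given for conduct problems. The SAP states no purpose for the secondary binary versions, so a reader might infer that they exist to show movement out of a problem range, but the documents do not say so.
- A reader might also infer that benefit will be reported as harm. The documents do not support that. They set no common rule for reading signs, the secondary outcomes already mix directions (wellbeing is better when higher, hyperactivity when lower), and binary results are to be shown as risk ratios with natural frequencies, so the share flagged in each arm will be visible.
- Because the documents do not give the prosocial bands, it cannot be asserted that the scale has a high band in the intended sense. The wording may be loose shorthand. That would make the indicator undefined, which also needs correcting.

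**Conclusion.** The point holds in a limited form. The SAP states a rule that suits difficulty scales and applies it to a strength scale. Read literally, the prosocial indicator flags the favourable end, or a band that the documents do not define. It then runs opposite to the other SDQ indicators and cannot show movement out of the low-prosocial range, which is at odds with the reason given for dichotomising the primary outcome.

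The consequence is small. The binary version is an addition to one secondary outcome, and the continuous prosocial score is analysed as well. The protocol's analysis of mechanisms reports effects in standard deviation units and calls the evidence suggestive. It would therefore be wrong to conclude that the answer to research question 3 is compromised. The primary outcome and power are untouched.

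The conclusion about direction rests on the documents alone. The risk ratios rest on the assumed normal score, shifts and flagged shares, and show only that the choice of end matters. The wording should be corrected before analysis.

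**What to change.** In the Design overview of the SAP:

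1. Restrict the high-or-very-high rule to the emotional, peer and hyperactivity subscales.
2. Define the prosocial indicator as 1 at the unfavourable, low end. Take the cut-off from the SDQ categorisation that the sponsor uses and state it in the SAP before analysis. The documents do not give that cut-off, so none is proposed here.
3. Code the baseline value that enters the model in the same way.
4. State the favourable direction of each binary outcome in the results table.

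If the authors did intend an upper-end indicator, the SAP should say so, give its cut-off and declare it a favourable outcome. That would settle the definition, but low-prosocial young people would still not be identified.

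The cost is a short edit to the SAP, one recode in the analysis program and a table note. No data collection changes.

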### Sample size calculations overview

The expected analytical sample will have two features that are important to consider for inference:

- There will be a small number of units of randomisation (teams) within strata (LA): Among the 29 LAs participating in the whole evaluation (internal pilot + efficacy), the median number of teams per LA is 3 (the average 4.6), with all but 2 LAs having 10 or fewer teams involved in the trial (Brent has 12 teams and Barking and Dagenham has 21 teams).
- Units of randomisation (teams) have more than 10 observations on average: Based on the conservative predictions of participating young people provided by Local Authorities so far, the average expected number of participants per team is 13.

De Chaisemartin and Ramirez-Cueller (2024) show that in stratified cluster RCT where the number of units of randomisation (teams) is small (10 or fewer) within strata (Local Authorities), the regular practice of clustering standard errors at the unit of randomisation can lead to downward bias in estimates of the variance of the treatment effect, resulting in over-rejecting the null hypothesis (of no effect). They advise that standard errors should be clustered at the strata level (LA) when RCTs have this type of configuration (and this result holds whether or not strata fixed effects are controlled for).

We are not aware of any software allowing us to perform power calculations that take these issues into account. In order to account for the exact nature of our dataset and for these technical complexities, we therefore opted for calculating the Minimum Detectable Effect associated with 0.8 power via simulations programmed in STATA and adapting the procedure

<sup>6 Even after removing the 6 teams that recruited in the pilot but did not collect any endline data, the median number of teams per LA is also 3 (the average if 4.5).

<sup>7 After considering the actual attrition at endline in the pilot (54%) and the expected 30% attrition rate at endline in the efficacy, we would have 9.4 observations per team on average.

<sup>8 In cases where clusters are small (fewer than 10 observations per unit of randomisation on average), estimates of the standard errors should not adjust for degrees of freedom. This is not the case we expect even under the conservative projections in terms of participating young people.

suggested in McConnell and Vera-Hernandez (2015). The simulation code used to perform these calculations is enclosed but we describe the steps used to perform these simulations below.

Each simulation is characterised by five parameters:

- Standard deviation of the outcome (σ)
- Intra-cluster correlation (ρ)
- Minimum Detectable Effect (β)
- Attrition rate (r)
- A threshold on the continuous outcome above which the binary indicator takes the value 1 and 0 otherwise (η)

Each simulation is based the following steps:

- 1. Randomise teams to be newly randomised to treated or control within each LA with 50-50 split.
- In LAs that have an odd number of teams to randomise, we randomly select whether (n+1)/2 or (n-1)/2 teams would get treated (where n is the number of teams to randomise)
- 3. Generate a normally distributed random variable at the Local Authority level,  $\theta_j$ , of mean 0 and variance  $\rho\sigma^2$
- 4. Generate a normally distributed random variable at the young person level,  $\epsilon_{ij}$ , of mean 0 and variance  $(1 \rho_{-})\sigma^2$
- 5. Implement the following data generation process for the outcome Y:

$$Y_{ij} = \beta T_{ij} + \theta_j + \epsilon_{ij}$$

where  $T_{ij} = 1$  if participant *i* is recruited in a treated team and 0 in a control team

- 6. Create a binary outcome  $D_{ij}$  such that it takes the value 1 if the score above is above a particular threshold  $\eta^9$  and 0 otherwise
- 7. Estimate OLS regressions of the chosen outcome (continuous  $Y_{ij}$  or binary  $D_{ij}$ ) on the treatment dummy, clustering the standard errors at the LA level, with or without controlling for Local Authority fixed effects, on a randomly selected sample of observations of size (1-*r*) of the expected number of study participants in order to

<sup>9 This threshold is chosen such that the mean of D is equal to the probability of observing our primary outcome in the baseline pilot data.

<sup>10 This step is to report power calculations for the binary outcome based on the continuous score, though the data generating process assumed here only enables us to simulate average impacts on the continuous score and hence may miss possibly stronger impacts the intervention may have at the top of the distribution

simulate a random attrition rate *r* to which we add the 83 observations from pilot that have endline data.

8. Repeat steps 1 through 6 1000 times and compute the power as the proportion of times the coefficient  $\beta$  is significant at the 95% level.

As part of this exercise, we wanted to explore the power implications of controlling for a lagged (baseline) outcome. Instead of making additional assumptions to simulate such baseline outcome, we instead performed the simulation above with smaller values of the variance of the outcome variable and of the ICC in order to mimic the effect of controlling for a lagged outcome on these parameters as estimated using data from the pilot period.

